### **1.5. Indication that this clinical trial will be conducted in accordance with the protocol, these rules, and regulatory requirements.**

This clinical study will be conducted in accordance with this protocol, current principles of good clinical practice (ICH GCP), ethical principles of conducting medical research involving human subjects of the Helsinki Declaration of the World Medical Association, as well as all the requirements of regulatory authorities of the Russian Federation.

### **1.6. Description of study population**

Healthy eligible volunteers will participate in this study.

## 2. OBJECTIVES AND PURPOSES OF THE STUDY

The objective of this study was assessment of safety, reactogenicity, immunogenicity, and efficacy of quadrivalent inactivated subunit influenza vaccine Grippol® Quadri (NPO Petrovax Pharm, LLC, Russia) versus trivalent inactivated polymer-subunit vaccine Grippol® Plus (NPO Petrovax Pharm, LLC, Russia) in subjects from 18 to 60 years old.

### Study goals:

- Study and comparative assessment of immunogenicity of quadrivalent inactivated subunit influenza vaccine Grippol® Quadri versus trivalent inactivated polymer-subunit vaccine Grippol® Plus in subjects from 18 to 60 years old.
- Assessment of safety and reactogenicity of the quadrivalent inactivated subunit influenza vaccine Grippol® Quadri compared to the influenza vaccine trivalent inactivated polymer subunit vaccine Grippol® Plus in volunteers ages 18–60 years old.

Strictly confidential. Proprietary Information.  
[name]

- Study and comparative assessment of immunogenicity of quadrivalent inactivated subunit influenza vaccine Grippol® Quadri versus trivalent inactivated polymer-subunit vaccine Grippol® Plus in subjects from 18 to 60 years old.

### 3. STUDY DESIGN

#### 3.1. Primary and additional study parameters that will be evaluated during the study

##### **Primary immunological efficacy endpoint:**

- The share of subjects achieving seroconversion (the number of volunteers with antibody titer [of at least 1:40] increased more than 4-fold versus baseline [assessed by HAIR]) for antigens: influenza virus type A — H1N1, influenza virus type A — H3N2, influenza virus type B — Yamagata and Victoria lineage, based on assessment at Day 21 after immunization (Visit 7).

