#### **Serologic testing (serum antibody titer test):**

Immunological efficacy (antigenic activity) of the vaccine is evaluated by its ability to induce the specific immune response, which can be identified under laboratory conditions by serum antibody titer to each antigen.

Antibody titer is determined using the hemagglutination inhibition reaction (HAIR), the method recommended by the WHO for influenza vaccine efficacy evaluation. The study is conducted at the central laboratory. As an additional method for 150 volunteers (50 volunteers in each group), a microneutralization assay is planned (the data will be used to evaluate seroprotection). The detailed description of the study methods is provided in the laboratory guide.

Blood samples for antibody titer test and calculation of mean geometric antibody titer will be collected for determination of background antibody titer after the immunization (Visit 0, Screening) and evaluation of functional immune reaction three weeks after immunization (Visit 7, Day 22±1).

Study parameters:

- The share of subjects achieving seroconversion (the number of volunteers with antibody titer [of at least 1:40] increased more than 4-fold versus baseline [assessed by HAIR]) for antigens: influenza virus type A — H1N1, influenza virus type A — H3N2, influenza virus type B — Yamagata and Victoria lineages.

Strictly confidential. Proprietary Information.  
[name]

- Coefficient of increase of mean geometric antibody titer (antigens H1N1, H3N2, Yamagata and Victoria lineages) (assessed by HAIR).
- Geometric mean of serum antibody to antigens titer (assessed by HAIR): influenza virus type A — H1N1, influenza virus type A — H3N2, influenza virus type B — Yamagata and Victoria lineages.
- Seroprotection: share of subjects achieving protective antibody titer (1:40 and more, assessed by HAIR and microneutralization test) to antigens H1N1, H3N2, Yamagata and Victoria lineages.

The detailed instruction on blood and serum sampling, labeling of tubes, storage and transportation of samples is presented in a separate laboratory guide provided by the central laboratory.

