#### *Primary variable*

For comparison, the primary change in the proportion of persons with seroconversion (the ratio of the number of volunteers in whom the antibody titer [at least 1:40] increased by more than 4 times compared with the baseline [method of determination — hemagglutination-inhibition reaction]) according to an assessment 21 days after vaccination (Visit 7, Day 22 ± 1) the statistical hypothesis will be tested that the study vaccine is “not worse than” the comparator vaccines with an established 15 % limit of “not worse”.

---

Strictly confidential. Proprietary Information.  
[name]

$H_0: \pi_1 - \pi_2 \geq 0.15$   $H_A: \pi_1 - \pi_2 < 0.15$ ,

$\pi_1$  и  $\pi_2$  – the share of subjects achieving seroconversion for the reference vaccine and the test vaccine respectively.

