### Justification of the "non-inferiority margin":

In placebo-controlled studies of inactivated influenza vaccines, the seroconversion parameter in placebo group for the study antigens amounts to 0–1 %. The placebo does not contain the respective antigens, so it demonstrates no immunogenic activity [1].

Taking into account the expected seroconversion level in reference groups > 60 % and the minimum limit for influenza vaccines > 40 % of subjects achieving seroconversion, established by the guidelines for harmonization of requirements to influenza vaccine of the Committee for Proprietary Medicinal Products (CPMP), the non-inferiority margin 15 % is significantly below the superiority of the comparator over the placebo, which is appropriate.

For testing of non-inferiority null hypothesis for Grippol® Quadri and Grippol® Plus vaccines, taking into account the following parameters:

Strictly confidential. Proprietary Information.  
[name]

- Power: 80 %
- One-sided significance level: 2.5 %
- Non-inferiority margin: 15 %
- Expected share of subjects achieving seroconversion in Grippol® Plus group: 60 %
- Expected actual difference for the parameter in groups: 1 %

1 % of the calculated sample size for non-inferiority hypothesis, primary dichotomized parameter and uniform assignment into groups (1:1) is based on the following formula [5,6]:

$$n = \frac{(z_\alpha + z_\beta)^2}{(\delta - \Delta)^2} [\pi_1(1 - \pi_1) + \pi_2(1 - \pi_2)]$$

where  $n$  — the number of patients in each group being compared;

$\pi_1$  — percentage of subjects achieving seroconversion in the reference vaccine group;

$\pi_2$  — percentage of subjects achieving seroconversion in the test vaccine group;

$\Delta = \pi_1 - \pi_2$  — the expected difference between percentages of subjects achieving seroconversion in the reference vaccine and test vaccine groups;

$Z$  — critical values of standardized normal distribution;

$\delta$  — non-inferiority margin.

according to the calculation as per the given formula using software package PASS 12, there shall be at least 193 volunteers in each therapeutic group (579 volunteers in total).

Thus, the minimum required sample size should be: 193 volunteers in each of the three groups (579 volunteers in total).

Taking into account the dropout during the study (5 %), the required number of volunteers has to be increased to 204 per group (612 in total).

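### The primary endpoint requires a rise of more than 4-fold; on a two-fold titer scale this means at least 8-fold, and the plan does not say which rule the 60 % planning rate and the 40 % benchmark use

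*Combined protocol and SAP*

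**What the plan says.** Section 3.1 defines the primary endpoint by "the number of volunteers with antibody titer [of at least 1:40] increased more than 4-fold versus baseline". The Synopsis and Section 6.2 use the same wording. Section 8.1 (Primary variable) phrases it separately, but again as a strict inequality: "the antibody titer [at least 1:40] increased by more than 4 times compared with the baseline". The fold-rise is strict in all four places, while the titer condition beside it is inclusive. The documents nowhere say that an exact 4-fold rise counts.

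On the assay, Section 6.2 says only: "The detailed description of the study methods is provided in the laboratory guide". The dilution series and the value assigned below the lowest dilution are not given.

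Section 8.2 plans on "Expected share of subjects achieving seroconversion in Grippol® Plus group: 60" %, a 1-point true difference and a 15-point margin. Its margin justification refers to "the minimum limit for influenza vaccines > 40 % of subjects achieving seroconversion" and to a placebo rate of 0–1 %. No fold-rise definition is attached to the 60 % or the 40 % figure.

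**The concern.** Two-fold steps allow fold-rises of 1, 2, 4, 8 and so on only. A strict rule then removes a whole response category, the exact 4-fold rise, from the responders. This looks unintended, because the separate requirement of a titer of at least 1:40 then has little or nothing left to do.

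At stake is who counts as a responder on the primary endpoint of a registrational study. The planning figures are also affected. If the 60 % and 40 % figures come from an inclusive 4-fold rule and the endpoint is coded strictly, the margin rationale compares rates with different meanings. If the question stays open until titers are seen, the handling of exact 4-fold rises could be settled with knowledge of the results.

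**Working it through.** **1. The plan's own figure.** The Section 8.2 formula is n = (z_α + z_β)² / (δ − Δ)² × [π₁(1 − π₁) + π₂(1 − π₂)]. Its inputs, all from Section 8.2, are one-sided α 2.5 %, power 80 %, π₁ = 0.60, π₂ = 0.59, δ = 0.15 and Δ = 0.01.

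(1.960 + 0.842)² = 7.849; (0.14)² = 0.0196; 0.2400 + 0.2419 = 0.4819.

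n = 7.849 × 0.4819 / 0.0196 = 192.98, rounded up to 193. Then 193 / 0.95 = 203.2, rounded up to 204, and 3 × 204 = 612. All stated figures reproduce.

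**2. Who changes status.** Assume two-fold steps with 1:5 as the lowest coded value. The lowest post-vaccination titer that qualifies is:

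| Baseline | At least 4-fold and ≥ 1:40 | More than 4-fold and ≥ 1:40 |
|---|---|---|
| 1:5 | 1:40 | 1:40 |
| 1:10 | 1:40 | 1:80 |
| 1:20 | 1:80 | 1:160 |
| 1:40 | 1:160 | 1:320 |

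Only volunteers with a baseline of 1:10 or above and an exact 4-fold rise change status. Under the strict rule, any qualifying rise from 1:5 or above already reaches 1:40, so the floor excludes nobody. Under the inclusive rule it excludes the 1:5 to 1:20 responder.

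**3. Possible size of the shift.** The documents give no baseline titer distribution and no spread of rises, so a range is needed. Assumptions: log2 rise X is normal with mean μ and SD 1.0–2.0, the same at every baseline, and rounded down to whole steps; a share s of volunteers is coded 1:5 and the rest are at 1:10 or above; 60 % is the rate under the inclusive rule.

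- Inclusive rate: s·P(X ≥ 3) + (1 − s)·P(X ≥ 2) = 0.60, solved for μ.
- Strict rate: P(X ≥ 3), whatever the baseline.

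For example, with s = 0 and SD 1.0, μ = 2 + 0.253 = 2.253 and P(X ≥ 3) = 1 − Φ(0.747) = 22.8 %.

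| Share at 1:5 | Strict rate, SD 1.0 to 2.0 |
|---|---|
| 0 % | 23–40 % |
| 25 % | 31–45 % |
| 50 % | 42–50 % |
| 80 % | 53–56 % |
| 100 % | 60 % (no drop) |

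**4. Margin rationale.** At the planned rate, 60 − 15 = 45, above the 40 % benchmark. At a reference rate of 55 % the difference is exactly 40, at 50 % it is 35 and at 45 % it is 30. The placebo comparison is less sensitive: even at 23 %, the advantage over a 1 % placebo rate is 22 points, still more than 15.

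**5. Power.** Power at 193 per group is Φ(0.14 / SE − 1.960), with SE = √{[π₁(1 − π₁) + π₂(1 − π₂)] / 193} and π₂ = π₁ − 0.01.

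| Reference rate | Power at 193 | Formula n |
|---|---|---|
| 60 % | 80.0 % | 193 |
| 55 % | 78.9 % | 199 |
| 50 % | 78.5 % | 201 |
| 45 % | 79.0 % | 198 |
| 40 % | 80.3 % | 192 |

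The comparisons of Group A with pooled B and C (193 against 386) keep about 89 % power or more over this range. The binomial variance is nearly flat here, so sample size is not the issue.

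**The case against.** The strict rule is stated consistently four times, and the documents cannot show that it is a mistake. The text is evidently a translation (a Russian conjunction survives in Section 8.1), so a translation slip is possible but unproven. A redundant floor is a hint about intent, and it depends on nothing being coded below 1:5. The two-fold scale is itself assumed. All of this stands, and it is why the point is put conditionally.

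A reader might infer that the 60 % and 40 % figures definitely no longer fit the endpoint. The documents do not support that, because they do not give the fold-rise definition behind either figure. If both already use a strict rule, there is no mismatch. Nor can a single drop in the rate be quoted: volunteers coded 1:5 need 1:40 under either reading, so the shift depends on a baseline mix that is not documented.

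A reader might also infer that the vaccine could fail a 40 % minimum because of the wording. No such test exists in the plan. Section 8.1 decides only on whether the upper 95 % limit of reference minus test exceeds 0.15. Where the plan wants an absolute threshold it states one, as with 2.5 for the titer increase. Section 8.2 concludes that the margin is small against the advantage over placebo, and the margin stays below that advantage throughout the range. Subtracting 15 from 60 and comparing with 40 is arithmetic on the plan's inputs; the plan does not print it.

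Finally, the same rule applies in every arm, so the comparison remains like with like.

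These points limit the consequences. They do not settle whether a 1:10 to 1:40 responder counts, and the written rule says no.

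**Conclusion.** The point holds in a limited form. As written, and on a two-fold scale, the primary endpoint needs at least an 8-fold rise and counts every exact 4-fold rise from 1:10 or above as a non-response. With a lowest coded value of 1:5, the 1:40 floor is then idle.

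If 60 % is an inclusive-rule rate, the strict rate could be about 23–60 %: no drop if all volunteers start at 1:5, and about 42–50 % if half do. That range rests on the assumed SD of 1.0–2.0 and on the undocumented baseline mix. Once the reference rate is below 55 %, the part of the margin rationale that draws on the 40 % benchmark no longer has the room that the planned 60 % gives it.

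The wording does not make the trial materially underpowered, does not push the margin above the advantage over placebo, and does not create a 40 % hurdle for success. What needs correcting is the responder classification and the use of the 60 % and 40 % figures without a stated definition.

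**What to change.** Before unblinding, change the definition to a rise of at least 4-fold with a post-vaccination titer of at least 1:40 in all four places: the Synopsis, Section 3.1, Section 6.2 and Section 8.1. State the dilution series and the value assigned below the lowest dilution, and confirm that the 60 % and 40 % figures use the same definition.

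If the strict rule is truly intended, say so explicitly, and restate the 60 % assumption and the 40 %-based part of the margin rationale on that rule.

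Either route is a wording amendment. It needs no new data and no additional volunteers.

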##### **Secondary efficacy endpoints:**

- Coefficient of increase of mean geometric antibody titer (antigens H1N1, H3N2, Yamagata and Victoria lineage), based on assessment at Day 21 after immunization (Visit 7).
- Geometric mean of serum antibodies to antigens: influenza virus type A — H1N1, influenza virus type A — H3N2, influenza virus type B — Yamagata and Victoria lineage, based on assessment at Day 21 after immunization (Visit 7).
- Seroprotection: share of subjects achieving protective antibody titer (1:40 and more) to antigens H1N1, H3N2, Yamagata and Victoria lineage, based on assessment at Day 21 after immunization (Visit 7).
- Incidence of influenza and ARI based on assessment 180±5 days after immunization (Visit 12).
- Severity and duration of reported cases of influenza and ARI, complications.

##### **Safety parameters:**

The safety parameters of this study are the following:

- Quantitative assessment and nature (severity and duration) of local and systemic reactions to vaccine administration.
- AEs and SAEs associated with the study vaccines.
- Immediate type AEs emerging within 60 minutes after immunization.
- Incidence and nature of intercurrent disorders
- Vital function assessment results.
- Results of physical examination.
- Neurological examination results.
- Results of blood hematology and biochemistry tests.
- Urinalysis results.
- Immunological parameters evaluation results: serum immunoglobulin content (ELISA: IgE).

---

[figure not shown]
Strictly confidential. Proprietary Information.  
[name]

### **3.2. Description of the type / design of the study and a schematic representation of its design, procedures, and stages**

This was a phase II-III, 6-month, multicenter, double-blind, randomized comparative study of safety, reactogenicity, immunogenicity and efficacy of quadrivalent inactivated subunit influenza vaccine Grippol® Quadri versus trivalent inactivated polymer-subunit influenza vaccine Grippol® Plus in parallel groups in volunteers of 18 to 60 years. Study design flow and schedule of procedures are shown in Figure 1 and in Table 2.

Strictly confidential. Proprietary Information.  
[name]

**Figure 1. Schematic design of the study**

Strictly confidential. Proprietary Information.  
 [name]

**Table 2. Schematic design of study procedures and stages**

	Visit 0	Visit 1		Visit 2	Visit 3	Visit 4	Visit 5	Visit 6	Visit 7	Visit 8	Visit 9	Visit 10	Visit 11
	Screening	Immunization		Outpatient follow-up						Telephone call			
Day after immunization	Day (-3) – 0	Day 0	Before	Day 1	Day 2	Day 3	Day 4	Day 5	Day 22±1	Day 43±5	Day 64±5	Day 122±5	Day 180±5
Signing of informed consent	X												
Collection of demographic data and history	X												
Measurement of body weight, height, calculation of BMI	X												
Physical examination	X	X	X	X	X	X	X	X	X				
Vital signs assessment	X	X	X		X			X	X				
Body temperature measurement	X	X	X	X	X	X	X	X	X				
Complete blood count 	X				X				X				
Blood biochemistry test 	X				X				X				
Urinalysis 	X				X				X				
Tests for syphilis, HBV, HCV, HIV	X												
Urine test for pregnancy	X									X			
Serological test (serum antibody titer test)	X									X			
Immunoglobulins (IgE)		X								X			
Neurological examination		X			X								
Assessment of volunteer's compliance with inclusion and non-inclusion criteria	X	X											
Assessment for exclusion criteria	X	X	X	X	X	X	X	X	X	X	X	X	X
Randomization		X											
Immunization			X										
Distribution of volunteer's diaries and instructions 			X										
Review of volunteer's diary				X	X	X	X	X	X				
Return of volunteer's diaries										X			
Interviewing on ARI symptoms for the period										X	X	X	X
Recording of concomitant therapy	X	X	X	X	X	X	X	X	X	X	X	X	X
Recording of local and systemic reactions, adverse events, and intercurrent disorders		X	X	X	X	X	X	X	X	X	X	X	X

 - Hemoglobin, RBC, hematocrit, PLT, WBC and WBC differential (neutrophils, lymphocytes, monocytes, eosinophils, basophils), ESR.

 - Glucose, urea, creatinine, total bilirubin, total protein, ALT, AST, AP.

 - Relative density, protein, sugar, RBC, WBC.

 - Self-measurement of the body temperature by the volunteer, with the information logged into the diary.

---

Strictly confidential. Proprietary Information.  
[name]

### ***Screening (Visit 0 (-3), -0 days):***

Volunteers will be invited to participate in the study and undergo the corresponding screening procedures:

- Signing of the informed consent form for participation in the study.
- Collection of demographic data (age, gender, race).
- Collection of medical history, history of infections and previous immunizations.
- Physical examination, measurement of height, body weight (calculation of BMI, kg/m^2).
- Measurements of vital functions (pulse, SBP, DBP).
- Body temperature measurement (t°)
- Laboratory investigations:
  - Blood hematology (hemoglobin, RBCs, hematocrit, platelets, WBC and WBC differential [neutrophils, lymphocytes, monocytes, eosinophils, basophils], ESR).
  - Blood biochemistry (glucose, urea, creatinine, total bilirubin, total protein, ALT, AST, AP).
  - Urine test with sediment microscopy (specific density, protein, sugar, RBC, WBC).
  - Tests for syphilis, HBV, HCV, HIV infection.
  - Urine test for pregnancy (only for female subjects).
  - Blood collection for serology (baseline serum antibody titer).
- Preliminary assessment of volunteer's compliance with inclusion and non-inclusion criteria.
- Assessment for exclusion criteria.
- Recording of concomitant therapy within 3 months prior to screening, including collection of information on vaccinations within the last year.
- Oral instructions (in addition to volunteer's information leaflet) on not allowed medicinal drugs during screening and for the whole study period.

Within the study period, volunteers will not be allowed to take medicinal drugs listed in section 5.2.1.

The period of Screening could last up to 3 days. The duration has to be sufficient to obtain all the parameters required to assess the selection criteria. In the volunteer's best interests, procedures of Visit 0 and Visit 1 can be pooled on condition of collection of all the required parameters within one visit.

### ***Visit 1 (Immunization day):***

Final assessment of volunteer's eligibility, including measurement of the body temperature, is performed at Visit 1 before the procedure of randomization and before immunization.

If the volunteer meets all the inclusion criteria and none of the non-inclusion criteria, and if the volunteer did not take any of the unallowed drugs prior to the Screening visit, the volunteer is eligible for immunization.

---

Strictly confidential. Proprietary Information.  
[name]

The volunteer remains under the study doctor's observation within the first 2 hours after immunization.

*Therefore, the following procedures are performed at Visit 1:*

- Physical examination before immunization and 2 hours after immunization.
- Measurement of the body temperature ( $t^\circ$ ) before immunization and 2 hours after immunization.
- Measurement of vital signs (pulse, SBP, DBP) before immunization and 2 hours after immunization.
- Neurological examination before immunization.
- Laboratory investigations:
  - Blood collection prior to immunization to determine the baseline IgE level.
- Final conclusion on volunteer's compliance with inclusion and non-inclusion criteria.
- Randomization.
- Immunization.
- Provision of a volunteer's diary and instructions on keeping the diary (2 hours after immunization).
- Assessment for exclusion criteria (prior to immunization and 2 hours after immunization).
- Recording of concomitant therapy.
- Recording local and systemic reactions, adverse events, and intercurrent disorders.

After immunization and conclusion of follow-up (2 hours) the volunteer is instructed on how to keep a diary. The volunteer has to log the first records (body temperature in the morning) into the diary at the trial site to ensure that records in the diary are made correctly.

***Visit 2 (Day 1 after immunization):***

The following procedures are performed at Visit 2:

- Physical examination.
- Body temperature measurement ( $t^\circ$ ).
- Review of volunteer's diary.
- Assessment for exclusion criteria.
- Recording of concomitant therapy.
- Recording local and systemic reactions, adverse events, and intercurrent disorders.

